10.2.1. Handling of Withdrawals

Subjects will be free to withdraw from the study, including discontinuing investigational product administration, and further follow-up of the study at any time.

Should a request for early withdrawal from the study with no further follow-up be made, the subject should be encouraged to return to the study site for a last follow up visit and undergo all End-of-Study/Early-Termination assessments.

When a subject withdraws from the study prior to completing the End-of-Study Visit, the reason for withdrawal is to be documented on the eCRFs and in the source document.

10.2.2. Replacements

Subjects who discontinue participation in the study for any reason after dosing will not be replaced. The sample size was estimated to account for an assumed discontinuation rate of 15% by Week 8.

11. STATISTICAL METHODS

11.1. Introduction

Detailed methodology for summary and statistical analyses of the data collected in this study will be documented in a Statistical Analysis Plan (SAP). The SAP may appropriately modify the analyses specified in the protocol, as necessary.

11.2. Analysis Sets

The all enrolled set will include all subjects who sign an informed consent form.

The full analysis set (FAS) includes all randomized subjects, and they will be included in the group to which they were randomized.

The per-protocol analysis set (PP) includes all subjects in the full analysis set that provide TFI data at Weeks 4 and 8, and do not have any protocol deviations that may impact the outcome of the TFI overall score.

The safety analysis set includes all subjects who receive study treatment, and they will be included in the treatment group based on the treatment received.

The FAS and PP sets will be used for efficacy analyses. The safety analysis set will be used for all safety analyses.

11.3. Study Endpoints

11.3.1. Efficacy Endpoints

The primary endpoint for this study is the percentage of subjects achieving response, where response is defined as achieving at least a 13-point reduction from baseline in the TFI overall score at both Weeks 4 and 8.

Secondary endpoints include the following:

- Change from Baseline in the NRS ratings of tinnitus annoyance
- Change from Baseline in the NRS ratings of tinnitus loudness
- Change from Baseline in TFI total score
- Change from baseline in TFI subscale scores (Intrusiveness, Sense of Control, Cognitive, Sleep, Auditory, Relaxation, Quality of Life, Emotional)
- PGIC score

- Change from Baseline in SF-12 scores

11.3.2. Safety Endpoints

The safety endpoints include:

- Incidence of treatment-emergent adverse events
- Change from Baseline in tympanometry
- Change from Baseline in otoscopy
- Change from Baseline in audiometry
- Change from Baseline in suicidal ideation or behavior
- Incidence of concomitant medications
- Change from Baseline in vital signs and weight

11.4. Statistical Analyses

11.4.1. General

There will be two sets of analyses. The Primary analyses will be conducted after all subjects complete Week 8 of the study, with all planned analyses to be conducted with all data collected in the database at time of database freeze. There will be a final analysis conducted once all subjects complete Week 16 of the study, to include all data collected from all subjects across all time points.

All data collected will be summarized descriptively. Descriptive statistics for continuous data are number of subjects, mean, standard deviation, median, minimum, and maximum values. Descriptive statistics for categorical variables will include number of observations and percentages.

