5.3. Blinding

The study will be double-blinded. Each treatment syringe will be prepared according to the detailed instructions in the Pharmacy Manual.

In case of emergency, the blind should be broken for site personnel only if knowing the subject's treatment allocation would facilitate specific medical treatment. In all cases, the Investigator should consult with the medical monitor prior to unblinding, and if not possible as soon as it is practical after unblinding has occurred and treatment initiated.

If the blind is broken, the subject will continue to be followed and evaluated per-protocol. The date, time, and reason for the unblinding must be documented on the appropriate page of the eCRF.

The randomization schedule or blocking factor(s) will not be revealed to study subjects, Investigators, clinical staff, site managers or the Sponsor until all subjects have completed the study and the database has been finalized by the Sponsor.

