10. SUBJECT COMPLETION

10.1. Completion

Study subject participation is complete after Week 16 (Visit 6). Subjects who discontinue the study before completion of Week 16 (Visit 6) will not be considered to have completed the study.

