11.4.2.1. Primary Analyses

The primary endpoint is the percent of responders at Week 8, where subjects will be classified as responders if they achieve at least a 13-point reduction from baseline in the TFI overall score at both Weeks 4 and 8. The primary endpoint will be summarized descriptively by treatment group. The percentage of responders will be analyzed using the common risk difference between treatment groups and will be tested using a Mantel-Haenszel test controlling for study site, duration of tinnitus, and baseline TFI overall score. Specifically, comparison between OTO-313 and placebo will be made by testing the following hypothesis:

$$H_0: P_{\text{OTO-313}} = P_{\text{Placebo}} \text{ vs } H_A: P_{\text{OTO-313}} \neq P_{\text{Placebo}}$$

The primary analysis will be conducted for the comparison of OTO-313 and placebo, using a 2-sided test and an alpha level of 5%. The 95% confidence intervals (CI) around the common risk difference will also be provided.

Missing data for the primary endpoint will be imputed using a multiple imputation technique that will be described in detail in the SAP.

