11.4.2.2.1. Additional Responder Analyses

The following additional responder definitions will also be derived for Weeks 12 and 16:

- Week 12 responder #1: achieving at least a 13-point reduction from baseline in the TFI overall score at Weeks 8 and 12
- Week 12 responder #2: achieving at least a 13-point reduction from baseline in the TFI overall score at Weeks 4, 8, and 12
- Week 16 responder #1: achieving at least a 13-point reduction from baseline in the TFI overall score at Weeks 12 and 16
- Week 16 responder #2: achieving at least a 13-point reduction from baseline in the TFI overall score at Weeks 8, 12, and 16
- Week 16 responder #3: achieving at least a 13-point reduction from baseline in the TFI overall score at Weeks 4, 8, 12 and 16

These additional responder secondary endpoints will be analyzed in the same manner as the primary analysis as described in Section 11.4.2.1.

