14.4. Electronic Case Report Form (eCRF)

eCRFs will be completed by site staff for each subject. Access for data entry will be provided to designated site staff. All data must be entered into the eCRFs in English and signed and dated electronically by the Investigator.

The eCRFs should be completed by Investigator site staff at the time of the subject's visit, with the exception of results of tests performed outside the Investigator's office, so that the eCRFs always reflect the latest observations on the subjects participating in the study.

As the site staff enters data, discrepancies will be automatically generated within the Electronic Data Capture (EDC) system for the site staff to resolve immediately. In addition, as a result of data review by the Sponsor or designee, manual queries will be raised electronically in the EDC system. Queries may also be raised as a result of source data verification by the clinical monitor. All corrections will be made within the EDC system by the Investigator or other authorized study site personnel. The clinical monitor and data management teams will ensure appropriate resolution of queries. The Investigator must authorize changes to the efficacy and safety data recorded in the EDC system.

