14.7. Monitoring

The Sponsor or its representatives will perform monitoring visits (on-site and/or remote as permitted by local regulations) as frequently as necessary based on site activity to review protocol compliance, compare eCRFs with individual subject's medical records and clinic charts, and ensure that the study is being conducted according to pertinent regulatory requirements. The dates of the visits will be recorded by the monitor in a study center visit log to be kept at the site. Monitoring visits will be made according to the Clinical Monitoring Plan.

Prior to site screening of the initial subject, site-specific source documents will be compared to the eCRF, and any findings will be discussed with the Investigator.

At all visits, the monitor will compare the data entered onto the eCRFs with the hospital or clinic records (source documents) in accordance with the Clinical Monitoring Plan. The review of medical records will be performed in a manner that ensures subject confidentiality is maintained. At a minimum, source documentation must be available to substantiate proper informed consent procedures, adherence to protocol procedures, adequate reporting and follow-up of AEs, administration of concomitant medication, drug receipt/dispensing/return records, and investigational product administration information. The Sponsor expects that, during monitoring visits, the Investigator (and as appropriate, the study coordinator) will be available, the source documentation will be available, and a suitable environment will be provided for review of study-related documents.

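### Does the by-arm analysis at Week 8 break the blinding rule that runs to Week 16?

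*Combined protocol and SAP*

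**What the plan says.** Protocol Section 11.4.1 sets up two readouts. For the first, "The Primary analyses will be conducted after all subjects complete Week 8 of the study", covering every planned analysis on the data held at a database freeze. For the second, "There will be a final analysis conducted once all subjects complete Week 16 of the study".

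The first readout needs treatment codes. Section 11.4.2.1 states that "The primary endpoint will be summarized descriptively by treatment group" and then tests OTO-313 against placebo, two-sided at 5%.

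Section 5.3 names those who may not see the randomization schedule or blocking factors: subjects, Investigators, clinical staff, "site managers or the Sponsor until all subjects have completed the study and the database has been finalized by the Sponsor". Section 10.1 puts the end of a subject's participation at Visit 6, Week 16. The exceptions concern individual subjects only: emergency unblinding (Section 5.3) and unblinding for the Safety Review Committee (Section 14.6.1).

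Outcomes are still collected after Week 8: TFI and PGIC at Weeks 12 and 16, SF-12 at Week 16, and the daily ratings throughout (Sections 8.4.1 to 8.4.5). Section 11.4.2.2.1 uses the later TFI data: "The following additional responder definitions will also be derived for Weeks 12 and 16".

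**The concern.** Read together, the sections seem to ask for something that cannot be done. The Week 8 analysis needs the codes about eight weeks before the Sponsor may have them. Section 5.3 also waits for a finalized database, whereas Section 11.4.1 offers only a freeze. Neither individual-subject exception covers an efficacy readout, and no unblinded statistician is named.

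The Sponsor also stays active in the trial during that interval. Section 14.4 says that "as a result of data review by the Sponsor or designee, manual queries will be raised electronically in the EDC system", and Section 14.7 that "The Sponsor or its representatives will perform monitoring visits". If allocation or by-arm results reached people in contact with sites, or reached subjects, the remaining self-reported ratings could be coloured. The five Week 12 and 16 responder definitions would be among the outcomes affected. A second worry is that the final analysis covers all time points, and no sentence says which result governs if the primary endpoint is run again and differs.

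**Working it through.** **1. Can both rules be obeyed at once?**

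- Section 5.3 restricts who sees the randomization schedule. It does not mention aggregate tables.
- Its list is subjects, Investigators, clinical staff, site managers and the Sponsor. A contract research organization works on the trial (Section 14.6) and is not on the list.
- The IRT system dispenses numbered kits according to treatment assignment (Section 5.2.3), so the codes are already held outside the blinded groups.
- A statistician outside the Sponsor can therefore run the Week 8 analysis while the schedule stays sealed from everyone listed. Obeying both sections leads to that arrangement.

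**2. Which safeguards are already written?**

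- Section 5.2.2: all site personnel are blinded.
- Section 5.3: the schedule is sealed until Week 16 and a final database.
- Section 14.6: medical staff of the Sponsor and the contract research organization review blinded safety information.
- Section 11.4.1: the database is frozen before the analysis, and the Week 8 set carries the label of primary.

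Two things are missing: the name of the code holder, and a list of who may see aggregate Week 8 results.

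**3. Is the primary test affected?**

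The design figures in Section 11.5 are 43% against 18%, 60 per arm, two-sided 0.05. With pooled variance under the null:

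- Mean rate = (0.43 + 0.18)/2 = 0.305.
- Null standard error = √(2 × 0.305 × 0.695/60) = 0.0841.
- Alternative standard error = √(0.43 × 0.57/60 + 0.18 × 0.82/60) = 0.0809.
- Power = Φ[(0.25 − 1.96 × 0.0841)/0.0809] = 85.4%, against a stated figure of about 85%.
- Inflation for 15% discontinuation: 120/0.85 = 141.2, so 142, against 140 planned.

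Neither figure depends on who holds the codes. The response is defined at Weeks 4 and 8, both collected before the freeze, and the primary hypothesis has one planned test. Alpha and power do not move.

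**4. How many subjects could be exposed?**

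The nominal interval for the last subject is Day 113 − Day 57 = 56 days. With the visit windows it is 109 − 60 = 49 to 117 − 54 = 63 days.

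The protocol gives no accrual pattern and no lag from the last Week 8 visit to known results, so both are assumptions here. The synopsis gives a study period of about 20 months (87 weeks) and 18 to 22 weeks per subject, which leaves T = 87 − 22 = 65 to 87 − 18 = 69 weeks of accrual. With even accrual:

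Subjects owing Week 16 = 140 × (8 − lag)/T

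| Lag (weeks) | T = 65 | T = 69 |
|---|---|---|
| 0 | 17.2 | 16.2 |
| 2 | 12.9 | 12.2 |
| 4 | 8.6 | 8.1 |
| 8 | 0 | 0 |

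Section 10.2.2 assumes 15% discontinuation by Week 8. Multiplying by 0.85 gives 14.6 and 13.8 at zero lag, and 7.3 and 6.9 at four weeks. Zero lag is not realistic, because a freeze and a multiple imputation come first.

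Subjects owing Week 12 = 140 × (4 − lag)/T: 8.6 or 8.1 at zero lag, none at four weeks.

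Faster accrual raises the count. Before discontinuation, T = 52 gives 21.5 at zero lag and 10.8 at four weeks; T = 26 gives 43.1 and 21.5.

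**5. How far could the late responder endpoints move?**

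Four of the five definitions in Section 11.4.2.2.1 require a response at Week 8: both Week 12 definitions, and Week 16 definitions 2 and 3. A subject who had not responded at Week 8 cannot become a responder on any of them. Only Week 16 definition 1 (Weeks 12 and 16) is free of Week 8, and at a four-week lag its Week 12 half is already collected. The documents give no basis for a rate at which subjects would change status, so I put no figure on the bias.

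**The case for a change.** The best case for a change is that Section 5.3 is a protocol commitment on blinding, and a reader should not have to infer who is exempt from it. No one outside the Sponsor is named as code holder, and release of Week 8 results is not restricted. All planned analyses are run at the freeze, and these include subject listings (Sections 11.4.3.1 and 11.4.3.3); the text does not say whether the listings carry treatment codes. With 140 subjects at about 55 sites, an average of 140/55 = 2.5 per site, a table by site and arm could come close to showing individual allocations. Clarifying words would cost little and leave sample size and visits alone.

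Much of this stands as a matter of drafting. The text does not name the code holder or the readers of the aggregate results. Section 11.1 sends detailed methodology to an SAP whose text is not in the document supplied, so I cannot say whether it fills the gap.

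What does not stand is the step from an unnamed person to an unprotected trial. A listing or site table that revealed allocation to the Sponsor or a site would itself breach Section 5.3, so the rule against it exists. Likewise, Section 11.4.1 already labels the Week 8 set as primary, which tells the analyst which result leads.

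**Conclusion.** The mismatch in wording between Sections 5.3 and 11.4.1 is real, but it is not a contradiction. Following both as written keeps the Sponsor and sites blinded to Week 16 and places the Week 8 analysis with someone outside the listed parties. Naming that person, and the few who may see aggregate results, is ordinary operational detail that a competent team settles before the freeze.

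The primary data, the 5% test, the power of about 85% and the primary conclusion are unaffected. The remaining exposure concerns self-reported secondary outcomes without multiplicity adjustment (Section 11.4.2.2) in a Phase 2 trial, and it requires a leak. Its reach is about 7 to 9 subjects owing Week 16 at a four-week lag and none at eight weeks, assuming even accrual over 65 to 69 weeks; the lower end allows for the 15% discontinuation. Shorter accrual would raise these counts, but the need for a leak, and the lack of effect on the primary result, would remain. No change to the plan is called for.

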11.4.2. Efficacy Analyses

All efficacy endpoints will be summarized descriptively and analyzed using FAS. The primary endpoint will also be summarized descriptively and analyzed using PP.

11.4.2.1. Primary Analyses

The primary endpoint is the percent of responders at Week 8, where subjects will be classified as responders if they achieve at least a 13-point reduction from baseline in the TFI overall score at both Weeks 4 and 8. The primary endpoint will be summarized descriptively by treatment group. The percentage of responders will be analyzed using the common risk difference between treatment groups and will be tested using a Mantel-Haenszel test controlling for study site, duration of tinnitus, and baseline TFI overall score. Specifically, comparison between OTO-313 and placebo will be made by testing the following hypothesis:

$$H_0: P_{\text{OTO-313}} = P_{\text{Placebo}} \text{ vs } H_A: P_{\text{OTO-313}} \neq P_{\text{Placebo}}$$

The primary analysis will be conducted for the comparison of OTO-313 and placebo, using a 2-sided test and an alpha level of 5%. The 95% confidence intervals (CI) around the common risk difference will also be provided.

Missing data for the primary endpoint will be imputed using a multiple imputation technique that will be described in detail in the SAP.

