
Statistical Methods:
 
Sample Size Justification:
 
The primary endpoint is the percentage of responders, where response is defined as achieving at least a 13-point reduction from baseline in the TFI total score at both Weeks 4 and 8. It was observed from the previous study that the response rate for OTO-313 (0.32 mg) was 43%, and 13% for placebo. Based on these results, the assumed rate of response for OTO-313 is 43% and 18% for placebo, which is the 13% observed response rate in previous study plus 5% inflation for potential placebo response.
 
Assuming a 2-sided test and level of significance of 0.05, 60 subjects in the placebo group and 60 subjects in the OTO-313 group will provide approximately 85% power to detect a treatment difference in favor of OTO-313. It is also assumed that an observed discontinuation rate of 15% will be observed, hence the total sample size for this 2-arm study is planned to be 140 subjects, 70 subjects per arm. These sample size calculations were conducted using EASTv6.5 software with a test for a difference in proportions between two groups.
 
Analyses:
 
The primary endpoint, analyzed using the common risk difference between treatment groups, will be tested using a Mantel-Haenszel test controlling for duration of tinnitus and baseline TFI score at Week 8. The 95% confidence intervals (CI) around the common risk difference will be provided. The risk difference in responses rates will also be compared between treatment groups at Weeks 12 and 16 as secondary analyses.
 
The change from baseline in NRS Loudness, NRS Annoyance, TFI total score, each TFI subscale score, and SF-12 will each be analyzed using a linear mixed-effects model with treatment, study day, treatment-by-study day interaction, gender, and tinnitus duration as fixed effects. The unstructured covariance model will be used. Least-square adjusted means, the estimated difference in adjusted means between treatment groups and associated 95% CIs will be provided. Comparisons between treatment groups will be conducted at each post-baseline visit as secondary analyses.
 
The results of the PGIC will be analyzed using a Cochrane-Mantel-Haenszel mean score test controlling for baseline TFI score and duration of tinnitus. This will be done to compare OTO-313 with placebo.
 
Adverse events, audiometry, tympanometry, otoscopic, and C-SSRS safety endpoints will be summarized descriptively. Changes in vital signs and laboratory parameters will be summarized descriptively.
	

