4. STUDY POPULATION

4.1. General Considerations

Approximately 140 subjects will be enrolled at approximately 55 sites globally. Subjects will be eligible if they meet all of the following inclusion criteria and none of the exclusion criteria.

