11.5. Sample Size

The primary endpoint is the percentage of responders, where response is defined as achieving at least a 13-point reduction from baseline in the TFI total score at both Weeks 4 and 8. It was observed from the previous study (Study 313-201901) that the response rate for OTO-313 (0.32 mg) was 43% and 13% for placebo. Based on these results, the assumed rate of response for OTO-313 is 43% and 18% for placebo, which is the 13% observed response rate in previous study plus 5% inflation for potential placebo response.

Assuming a 2-sided test and level of significance of 0.05, 60 subjects in the placebo arm and 60 subjects in each of the OTO-313 arms will provide approximately 85% power to detect a treatment difference in favor of OTO-313. It is also assumed that an observed discontinuation rate of 15% will be observed, hence the total sample size is planned to be 140 subjects, 70 subjects per arm. These sample size calculations were conducted using EASTv6.5 software with a test for a difference in proportions between two groups.

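### The primary Mantel-Haenszel test is defined two ways, with and without study site as a stratum, and the 85% power was computed for neither

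*Combined protocol and SAP*

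**What the plan says.** Section 11.4.2.1 analyses the responder percentage through the common risk difference, "tested using a Mantel-Haenszel test controlling for study site, duration of tinnitus, and baseline TFI overall score". It uses a two-sided 5% level and adds that "The 95% confidence intervals (CI) around the common risk difference will also be provided". Under Statistical Methods, the Synopsis says the same endpoint is "tested using a Mantel-Haenszel test controlling for duration of tinnitus and baseline TFI score at Week 8"; study site is absent.

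Section 11.5 states that "60 subjects in the placebo arm and 60 subjects in each of the OTO-313 arms will provide approximately 85% power", for response rates of 43% and 18%, and that the calculation was done "using EASTv6.5 software with a test for a difference in proportions between two groups". It mentions no strata.

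Section 4.1 gives the scale: "Approximately 140 subjects will be enrolled at approximately 55 sites globally". Section 5.2.3 stratifies the permuted-block randomization by site, duration (two categories) and the average of the Screening and Baseline TFI (two categories). It gives no block size. Section 11.1 leaves detailed methods to a SAP, which may modify the analyses. The document contains no separate SAP text that settles this point.

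**The concern.** Both descriptions are current text for the single primary test, and they are not interchangeable. With about 55 sites and 140 subjects, adding site to the strata leaves most cells with very few subjects. The two versions can therefore reach opposite conclusions on the same data. With both on file, choosing one after the data are seen would expose the primary result to challenge.

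The conflict reaches other analyses:

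- The five further responder definitions in Section 11.4.2.2.1 inherit the Section 11.4.2.1 test.
- Section 11.4.2 repeats the primary analysis in the per-protocol (PP) set: "The primary endpoint will also be summarized descriptively and analyzed using PP".
- The PGIC test has the same mismatch: site is in Section 11.4.2.2.3 but not in the Synopsis.
- As a lesser point, the mixed model has site and baseline TFI as covariates in Section 11.4.2.2.2, while the Synopsis has gender in place of both.

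**Working it through.** **1. The plan's own figure.** Inputs from Section 11.5: p1 = 0.43, p0 = 0.18, two-sided alpha 0.05, n = 60 per arm. For an unstratified test with pooled variance:

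- Mean rate = (0.43 + 0.18)/2 = 0.305.
- SE under the null = sqrt(2 x 0.305 x 0.695/60) = 0.0841.
- SE under the alternative = sqrt((0.43 x 0.57 + 0.18 x 0.82)/60) = 0.0809.
- Power = Phi((0.25 - 1.96 x 0.0841)/0.0809) = 85.4%.

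The stated 85% is reproduced as an unstratified test. The same formula with 70 per arm gives 90.3%.

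**2. Number of cells.** Neither description says how baseline TFI enters the strata. Assume two levels, as in the randomization. The Synopsis test then has 2 x 2 = 4 cells. The Section 11.4.2.1 test, with sites unpooled, has up to 55 x 2 x 2 = 220 cells, or 140/220 = 0.64 subjects per cell.

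**3. Why sparse cells lose information.** In a cell with n1 and n0 subjects per arm and n = n1 + n0, the Mantel-Haenszel weight for the risk difference is n1 x n0/n. The variance term of the test is n1 x n0 x m(n - m)/[n^2 (n - 1)], where m is the number of responders. If n1 or n0 is zero, both are zero and observed minus expected is zero. The cell's subjects drop out.

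**4. Simulation.** 43% versus 18%; permuted blocks within site x duration x TFI; Cochran-Mantel-Haenszel test without continuity correction; 3,000-4,000 runs per scenario. In the 120 case, 20 of 140 randomized subjects are removed at random. Assumed, because the documents do not give them: block size 2, 4 or 6; enrolment over 55 sites from equal probability to very steep; duration and TFI splits of 50:50 or 30:70.

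Power of the site-stratified test, 50:50 splits, block 2 / block 4:

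| Enrolment over 55 sites | 140 analysed | 120 analysed |
|---|---|---|
| Equal probability | 57% / 46% | 44% / 34% |
| Top 11 sites hold 45% | 66% / 58% | 52% / 47% |
| Top 11 sites hold 72% | 77% / 72% | 68% / 63% |
| Top 11 sites hold 89% | 84% / 83% | 75% / 75% |

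With 30:70 splits the range is 54-85% at 140 and 42-78% at 120. With block 6 and 50:50 splits, equal probability and the steepest enrolment give 42% and 81% at 140, and 32% and 74% at 120.

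Over all these scenarios:

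| | 140 analysed | 120 analysed |
|---|---|---|
| Unstratified | 90% | 85% |
| Four cells | 89-91% | 84-87% |
| Site in strata, unpooled | 42-85% | 32-78% |
| Subjects at zero weight (site in strata) | 17-68% | 18-72% |
| Sites pooled into 5 groups x 4 cells | 86-90% | 78-84% |
| Mean 95% CI half-width, four cells | 15 points | 16 points |
| Mean 95% CI half-width, site in strata | 16-26 points | 17.5-29 points |

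The interval widths use the Sato variance of the Mantel-Haenszel risk difference.

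**5. Disagreement.** One test is significant at 5% and the other is not in about 8-50% of trials at 140 and 12-55% at 120. Only the site-stratified test is significant in about 2% of trials or fewer.

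**6. Relevance of 120.** It is the basis of the 85%, and it is close to the PP analysis. That set "includes all subjects in the full analysis set that provide TFI data at Weeks 4 and 8", and 15% loss by Week 8 (Section 10.2.2) leaves 140 x 0.85 = 119, before any exclusion for deviations.

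**7. Outside these scenarios** (block 2 / block 4). Exactly 2-3 subjects at every site gives 47% / 35% at 140 and 36% / 26% at 120. All subjects from 12 sites gives 88% / 86% and 79% / 77%. All from 5 sites gives 85% / 84% at 120. The ranges above are therefore not bounds.

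**The case against.** **The 85% is sound for the Synopsis test, and planning on an unstratified test is ordinary practice.** This stands. The power problem concerns only the Section 11.4.2.1 version.

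**Section 11.1 defers to a SAP, which may pool sites.** This stands as a limit on the power loss; the absence of a pooling rule cannot be established. It does not remove the conflict between two current definitions, and Section 11.1 does not undertake to resolve it.

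**The size of the loss rests on assumptions.** It does, and so do the disagreement rates. The direction does not: in every 55-site scenario run, the site-stratified test had less power.

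**The plan analyses a risk difference, so the test might use its own variance.** In a separate run with 120 randomized, Sato variance gave 44-52% instead of 35-46% with equal-probability enrolment, and 58-64% instead of 54-60% with uneven enrolment. The gap narrows but remains. Letting site response rates vary by 18 points either way usually added a few points to the site-stratified power, again without closing the gap.

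**The primary analysis uses all randomized subjects with multiple imputation.** Imputation was not modelled, so the 140 figures treat every response as observed. The loss appears at both 140 and 120.

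**Site is a randomization factor, so controlling for it has a rationale.** True, and pooled sites meet it at little cost in power.

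**Conclusion.** The concern holds and needs correction before unblinding. The conflict between Section 11.4.2.1 and the Synopsis is plain from the text and needs no assumption. The 85% in Section 11.5 is correct for an unstratified two-proportion test with 60 per arm and remains a fair approximation for a four-cell test.

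It does not describe a test stratified by unpooled site. Under the assumed scenarios, that version loses between about 5 and nearly 50 percentage points of power against four cells, and the choice between versions can decide the primary result. This loss is conditional on literal, unpooled use of about 55 sites and two-level TFI.

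**What to change.** State one primary test, in the same words, in the Synopsis and Section 11.4.2.1. There are two workable options:

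- Remove study site from the Mantel-Haenszel strata and use the four randomization cells: duration category by category of the averaged Screening and Baseline TFI. Say explicitly that this average, not the Baseline score alone, defines the stratum. Close the gap between the two TFI categories, since an average of 53.5 falls in neither as written.
- Keep site, with a prespecified rule, applied blind, that pools sites into a few groups.

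Carry the chosen strata to the responder analyses in Section 11.4.2.2.1 and to PGIC in Section 11.4.2.2.3 and the Synopsis. In Section 11.5, state the test and number analysed to which the 85% refers. Also reconcile the mixed-model covariates between Section 11.4.2.2.2 and the Synopsis.

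The cost is protocol and SAP wording; visits, data and sample size do not change, and randomization may stay stratified by site. The small downside of the first option is that the test no longer conditions on individual site. Type I error was simulated at 30.5% response in both arms with 140 analysed, with site rates equal or assumed uniform from 5.5% to 55.5% (6,000-8,000 runs per scenario). It was 4.1-5.5% with four cells, 4.2-5.4% with five pooled groups and 4.1-5.2% with 220 cells.
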